4.4. Data collection

Infants meeting all of the inclusion criteria will have *de-identified* information collected on selected characteristics of mother, delivery and infant. This information will allow a comparison of randomised and non-randomised infants to determine the impact on generalizability of exclusions, infants where consent was not sought for some reason, and infants where consent was refused. Infants that are randomised will also have their randomisation number recorded on the form, allowing linkage to data collected in the study. Annex A lists the variables on which data will be collected on infants meeting all inclusion criteria.

Infants that are randomised will have additional detailed information collected on the course of treatment, and on all key primary and secondary outcomes. Annex B lists the variables on which data will be collected on randomised infants.

Information from the data collections forms will be entered into a password protected online database operated by the Australian Pediatric Trials Network ('WebSpirit') which will be accessed through the Ramaiah Hospital computer network, accessible to study administrators; the database includes an FDA-compliant audit mechanism which tracks all data queries and modifications after initial entry. The database will not contain any names or addresses, only Study ID numbers and Medical Record Numbers (MRNs). A listing of Study ID numbers will be linked to names, addresses and contact numbers in paper records kept in a locked filing cabinet in the Medical Records Department of Ramaiah Medical College, until results are published.

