- Damage to nares: A standard measurement protocol will be introduced which governs the process for diagnosing damaged nares;
- Pneumothorax: The treating clinician will order and interpret the X-ray for clinical purposes, but the X-rays will be provided to the radiologist for independent verification, blinded to treatment arm;
- IVH/ICH/PVL: The consultant radiologist will undertake the scans for IVH/ICH/PVL, but it is not possible to blind to study allocation.
- $\text{FiO}_2 \geq 60\%$: This is made objective by having the same saturation targeting protocol for both treatment groups (90-95% by SpO_2), and by requiring that the oxygen requirement is maintained for one hour or more;
- Intubation & ventilation: This may be subjective and will therefore be interpreted alongside the objective indicator of a high oxygen requirement ($\geq 60\%$ for ≥ 1 hour);
- Surfactant: This may be subjective and will therefore be interpreted alongside the objective indicator of a high oxygen requirement and chest X-Ray result ($\text{FiO}_2 > 40\%$ to achieve 90-95% SpO_2 , with chest X-Ray suggestive of RDS); and
- Death prior to hospital discharge: This is an objective indicator unless infants are routinely discharged home moribund, which occurs in some low resource settings (to avoid mortuary costs), but which is not practised at Ramaiah Medical College.

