A standard clinical protocol will be prepared for the study, based on existing clinical practice at Ramaiah Medical College, which will apply equally to both treatment groups. The clinical protocol will specify:

1. Standard prong sizes to be used, by infant weight;
2. The SpO₂ range to be targeted;
3. The timing of obligatory outcome measurements (baseline, 6, 12, 24, 48 and 72 hours) and how they should be conducted, and how measurement complications should be managed if they arise (e.g., how long to delay with scheduled measurement of respiratory rate if infant is crying; how to address missed measurement) – this includes:
 - a. FiO₂;
 - b. SpO₂;
 - c. Respiratory rate; and
 - d. Arterial blood gasses, including pH, PaO₂, and PaCO₂.
4. Procedures governing the diagnosis and treatment of all adverse events, specifically:
 - a. Identification and confirmation of damage to the septum and nares;
 - b. Determining the need for screening for pneumothorax, and the process for blinded verification; and
 - c. Determining the need for cranial ultrasound, and the process for (unblended) diagnosis of IVH or ICH or PVL.
5. A clinical algorithm for managing all aspects of CPAP provision, including:
 - a. FiO₂ and PEEP, including starting points and rules governing stepping up and stepping down of these (including order, and size of increment);
 - b. Transfer to intubation and ventilation; and/or
 - c. Weaning from CPAP; and/or
 - d. Rules covering re-commencement of CPAP.

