Statistical Analysis Plan

“Randomised trial comparing CPAP machines with reusable vs disposable circuits”

Introduction

1. This document sets out the statistical analysis plan for a randomised trial conducted at Ramaiah Medical College hospital, Bangalore, Karnataka, India, between June 2017 and July 2018 (inclusive). At each point, the plan sets out the text in the original plan and highlights any variations from that plan, as updated on 31 August 2019.
2. **Limitations:** There were two important limitations to the study analysis as envisaged in the protocol:
 - a. The achieved sample size was n=51. This compares to the 80 randomised infants planned for as a feasible target in the setting, despite a 5-month extension to recruitment. The planned sample size was only capable of estimating a major difference (a difference of 0.70 standard deviations between the means) in the primary outcome. The achieved sample size therefore substantially reduces the study power.
 - b. Many of the outcomes, including the primary outcome, were predicated on the assumption that staff would be targeting oxygen saturations of 90-95%, as measured through pulse oximetry (SpO_2); it transpired that this was rarely the case. SpO_2 within the 90-95% target range was achieved in 54 of 224 readings (24.1%) overall, by reading:
 - 14 of 51 (27.5%) of readings at baseline;
 - 9 of 50 (18.0%) of readings at 6 hours;
 - 9 of 49 (18.4%) of readings at 12 hours;
 - 15 of 41 (36.6%) of readings at 24 hours;
 - 4 of 24 (16.7%) of readings at 48 hours; and
 - 3 of 9 (33.3%) of readings at 72 hours.

Exclusion of other outcomes SpO_2 was outside the target readings would have markedly reduced the sample size available, so analysis was continued as planned, including all records, with a note that the analysis may be contaminated. In the case of the primary outcome, for example, the analysis interprets the amount of oxygen required as being reflective of that needed to achieve targeted saturations; when the SpO_2 is above the target range, it is difficult to ascribe meaning to the oxygen level that was provided.

Primary outcome

3. **Descriptive analysis as specified in the protocol:**

Primary and selected secondary outcomes - descriptive: The raw values of the primary outcome (FiO_2) and five secondary outcomes (SpO_2 , respiratory rate, pH, PaO_2 , $PaCO_2$) will be graphed to allow visual comparison of differences at baseline and over time. [Protocol, para 5.2]

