- a. As with the primary endpoint, change from baseline at the 6-hour reading was adopted as the preferred analysis for SpO₂ (Secondary outcome #2), respiratory rate (Secondary outcome #3), pH, PaO₂, PaCO₂ (all reported as part of Secondary outcome #4) and duration of CPAP (Secondary outcome #8). Due to concerns about non-normality, van Elteren's extension to the Wilcoxon test was used to assess statistical significance, while controlling for stratification by gestational age group. No testing was performed for Secondary outcome #4 (pH, PaO₂, PaCO₂) as there were only five infants who had readings at both baseline and six hours of age.
- b. Dichotomous secondary outcomes were compared using the Cochran-Mantel-Haenszel test, with assessment for homogeneity using the Breslow-Day test. The exceptions to this were:
 - Where there were no events in one stratum (i.e., CPAP failure [Secondary outcome #5], Serious Adverse Event [Secondary outcome #9], Intubation and mechanical ventilation [Secondary outcome #15] and Death [Secondary outcome #17]), Fisher's Exact test was used on the full data; and
 - Where there were no events in either stratum (Damage to the nasal septum [Secondary outcome #10], Damage to the nares [Secondary outcome #11], Pneumothorax

Statistical Analysis Plan

“Randomised trial comparing CPAP machines with reusable vs disposable circuits”

diagnosed by X-Ray [Secondary outcome #12], Intra-ventricular haemorrhage (IVH), intra-cranial haemorrhage (ICH), or periventricular leukomalacia (PVL) as diagnosed by cranial ultrasound scan [Secondary outcome #13], $\text{FiO}_2 \geq 60\%$ to maintain SpO_2 at 90-95% for one hour or more, during CPAP treatment [Secondary outcome #14] and, for infants born at 28+0 to 33+6 weeks' gestation, oxygen dependent at 36 weeks' gestation [Secondary outcome #16]), no statistical test was performed.

Other issues

11. **Multiple comparisons:** The principal control for multiple comparisons was the designation of a single primary endpoint.

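### Zero events are reported for pneumothorax, brain imaging findings and 36-week oxygen dependence without the number of infants assessed, and the listed data items cannot supply it

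*SAP*

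**What the plan says.** SAP para 10b compares dichotomous secondary outcomes by Cochran-Mantel-Haenszel test, with two exceptions. The second begins "Where there were no events in either stratum" and covers #12, #13 and #16 among others. It ends "oxygen dependent at 36 weeks' gestation [Secondary outcome #16]), no statistical test was performed". No denominator, rate or interval is given. SAP para 2a gives the total: "The achieved sample size was n=51".

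On who is assessed, Protocol 6.2 (item 4) leaves the rules to a clinical protocol that is not among the documents. For #12 that protocol covers "Determining the need for screening for pneumothorax, and the process for blinded verification"; for #13, "Determining the need for cranial ultrasound, and the process for (unblended) diagnosis of IVH or ICH or PVL". Protocol 4.5 adds for #12 that "The treating clinician will order and interpret the X-ray for clinical purposes", with a radiologist verifying the film blind to arm. It says that the cranial scans cannot be blinded. Protocol 4.3 says that the machines are visibly different.

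On what is recorded, Protocol 4.4 promises data on all key outcomes and states: "Annex B lists the variables on which data will be collected on randomised infants". Annex B provides an adverse event form completed once per event, and a general form completed once per infant.

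**The concern.** An outcome found by imaging can be counted only in infants who were imaged. If imaging follows need, a zero may mean that infants were examined and were normal, or that few were examined. The two carry very different safety information, and the reader cannot tell which applies. The staff ordering the X-ray know the arm, so the amount of looking could also differ between arms unseen.

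For #16 the difficulty is follow-up. The outcome is fixed at 36 weeks, some infants may have died or left hospital before then, and no listed item records oxygen status on that date.

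Monitoring side effects and adverse events is part of the stated aim (Protocol, Trial Summary, item 1), and no DSMB was planned (Protocol 4.6). The zero counts therefore carry a good part of what the trial can say about safety.

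**Working it through.** **1. The plan's own figure.** The SAP states zero events for #12, #13 and #16. With no denominator given, there is no rate to reproduce.

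**2. Can Annex B supply the number assessed?**

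| Outcome | Listed items that bear on it | What is not listed |
|---|---|---|
| #12 pneumothorax | Adverse event type; final diagnosis of the early respiratory distress, with pneumothorax or air leak as an option; chest X-ray diagnosis before surfactant | Whether an X-ray was taken in other infants |
| #13 IVH/ICH/PVL | Adverse event type, with grade for IVH | Whether a cranial ultrasound was done |
| #16 oxygen at 36 weeks | Total hours of passive oxygen and of ventilation; discharge dates; outcome at discharge | Oxygen status at 36 weeks; it is not a named adverse event type either |

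For #12 and #13 the items show positive findings. Outside infants given surfactant, a negative finding and no examination leave the same trace.

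**3. Timing for #16.** Infants born at 28+0 to 33+6 weeks are eligible.
- Born at 28+0: 36 × 7 − 28 × 7 = 252 − 196 = 56 days to 36+0 weeks.
- Born at 33+6: 252 − (33 × 7 + 6) = 252 − 237 = 15 days.

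Status is therefore needed 15 to 56 days after birth, while listed collection ends at hospital discharge. SAP para 6 reports two infants discharged before 72 hours, one against medical advice. Their stratum is not stated.

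**4. Deaths.** Para 10b says that death and CPAP failure each had no events in one stratum, so each had at least one in the other. Para 6 reports four failures within 72 hours (three Dolphin, one Fisher & Paykel) and none in the older group. The empty stratum for CPAP failure must then be the older one. Protocol 3.3 counts death as CPAP failure, so the deaths fall in the younger stratum, the one eligible for #16. This step assumes that any death before discharge counted as CPAP failure. The number, arm and timing of deaths are not given, and no rule states how a death before 36 weeks enters #16.

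**5. What zero events can exclude.** The exact two-sided 95% upper limit for 0/n is 1 − 0.025^(1/n). The arm sizes are not given; 51/2 = 25.5, so 25 stands for roughly one full arm. The smaller values are assumptions.

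| n assessed | Upper limit |
|---|---|
| 51 (both arms, all assessed) | 7.0% |
| 25 (about one arm, all assessed) | 13.7% |
| 15 | 21.8% |
| 10 | 30.8% |

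A limit based on imaged infants describes those infants. It extends to the whole arm only if they are representative of it.

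**6. Practice elsewhere in the SAP.** Para 2b gives the number of SpO₂ readings at each time. Para 10a says that only five infants had paired blood gases. Para 6 removes discharged infants from the survival denominators. The zero-event outcomes have no counterpart.

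**The case against.** A reader might infer that infants who were never scanned were counted as event-free, and that the zeros rest on a wrong denominator. The documents do not support this. Para 10b states no denominator and does not say how unassessed infants, or infants who died before 36 weeks, were treated. It mentions the zeros only to explain why no test was run.

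Other points on that side also stand. The unseen clinical protocol was to apply equally to both arms, and its screening rule might cover every infant or a whole gestation group. Annex B lists variables, and the forms themselves may hold more. #12 has a per-infant diagnosis field as well as the adverse event form, and every film taken was to be verified blind to arm. For #16, discharge home before 36 weeks, or zero hours of oxygen and ventilation, would settle many infants. With no #16 events in either arm, neither machine looks better on it, and death is tested separately as #17.

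Restricting #12 and #13 to imaged infants would be a poor remedy. It conditions on a step taken after randomisation by staff who know the arm, and would probably select the sicker infants. All randomised infants is a legitimate denominator for a clinically detected event.

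Finally, these are untested secondary outcomes in a study that SAP para 11 calls exploratory, and even full assessment leaves a limit near 14% per arm.

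None of this supplies the number assessed. Blinded verification covers only films that were taken, and the final-diagnosis field does not show that an X-ray was done.

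**Conclusion.** The concern holds as a gap in the data items and in the reporting. The listed variables cannot separate no event from not assessed for #12 and #13, and cannot fully yield #16. SAP para 10b reports zeros for all three without saying how many infants could have shown an event. Whether any count is wrong, or imaging differed between arms, cannot be judged from the documents.

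The effect is on how much safety the zeros can be taken to show. Per arm, the upper limit is about 14% if 25 infants were assessed and rises to 22% at 15 and 31% at 10, with n assumed throughout. For #16 the denominator cannot exceed the younger-stratum infants alive at 36 weeks. Describing its zero as holding in either stratum does not fit an outcome defined in one.

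This should be corrected before the zeros are presented as safety findings. It does not touch the primary analysis.

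**What to change.** In SAP para 10b:

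- **#12 and #13:** keep all randomised infants as the main denominator. Beside each count give, by arm, the number with at least one chest X-ray (#12) or cranial ultrasound (#13) during the stay, taken from radiology records by medical record number. Give exact upper limits for 0/n on both denominators, and show infants not imaged as a separate count. Do not redefine the outcomes among imaged infants.
- **#16:** report by arm the infants born at 28+0 to 33+6 weeks who were alive with known oxygen status at 36 weeks, from chart or discharge records. Show unknowns separately and remove the reference to either stratum.
- **Composite:** add death before 36 weeks or oxygen dependence at 36 weeks, over all infants randomised in that stratum. Label it as added after the data were seen.

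Recruitment ended in July 2018, so the missing Annex B items become retrospective extraction fields: X-ray done, cranial ultrasound done, and oxygen status at 36 weeks.

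The cost is a look-up of existing records for 51 infants and a few lines of SAP text. No new scans are involved. The likely downside is smaller assessed numbers and a less favourable safety statement. If nearly all infants prove to have been assessed, the zeros become more credible.

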- d) Infants clinically suspected to have another specified serious condition as their main disease process, ***diagnosed prior to randomisation***, specifically: cardiac anomaly, other congenital malformation with respiratory sequelae, septicaemia, pulmonary haemorrhage, pneumothorax, meningitis, poor respiratory effort or recurrent apnoea, or brain haemorrhage (IVH Grades III or IV);
- e) Infants who have an airway abnormality precluding the use of the standard CPAP interface proposed for this study (e.g., Pierre-Robin sequence, cleft lip or cleft palate) or who have a neuromuscular condition that interferes with respiration;
- f) Any infant whose treating clinician believes should not be randomised due to some other condition, or for any other reason (reason to be documented).

3.2. ***Primary outcome***

The primary outcome will be a comparison of fraction of inspired oxygen (FiO₂), measured as a change from baseline at 6, 12, 24, 48 and 72 hours after treatment commencement.

3.3. ***Secondary outcomes***

A range of secondary outcomes will be assessed:

- Oxygen saturation by pulse oximetry (SpO₂), measured as a change from baseline at 6, 12, 24, 48 and 72 hours after treatment commencement;
- Respiratory rate (breaths/minute), measured as a change from baseline at 6, 12, 24, 48 and 72 hours after treatment commencement;
- Arterial blood gas analyses, measured as a change from baseline at 6, 12, 24, 48 and 72 hours after treatment commencement, including:
 - pH;
 - Partial pressure of oxygen (PaO₂); and
 - Partial pressure of carbon dioxide (PaCO₂).
- CPAP failure (death or need for intubation and mechanical ventilation as demonstrated by an FiO₂ requirement $\geq 60\%$ for ≥ 1 hour to maintain SpO₂ at 90-95%);

- Surfactant provided when $\text{FiO}_2 > 40\%$ to maintain SpO_2 at 90-95% for ≥ 30 minutes, with RDS confirmed by chest X-Ray, in line with current Ramaiah standard practice;
- An omnibus indicator comprising CPAP failure or surfactant provision;
- Duration of CPAP treatment (hours) in infants that do not fail CPAP;
- Selected complications of treatment will be evaluated as sentinel outcomes. These, include:
 - Damage to the nasal septum;
 - Damage to the nares;
 - Pneumothorax as diagnosed by X-ray;
 - Intra-ventricular haemorrhage (IVH), intra-cranial haemorrhage (ICH), or periventricular leukomalacia (PVL) as diagnosed by cranial ultrasound scan;

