Block randomisation with variable block sizes will be used within each of two gestational age strata: $28^{+0}-33^{+6}$ weeks' gestation and $34^{+0}-36^{+6}$ weeks' gestation. These gestational age strata are chosen to reduce the possibility of a chance imbalance in gestational ages between the intervention and controls groups, post-randomisation, as the severity of RDS is inversely related to gestation. Infants of multiple births, of which more than one infant are eligible, will be randomised individually.

The order of the block sizes (4, 6, or 8) will be randomly selected and the assignment of will be random within each block, until the selection is forced. Random numbers will be generated by SAS 9.4 using randomly selected seed numbers; the seed will be selected by opening a large book and choosing left or right page by coin toss (heads=right).

Ramaiah hospitals will be provided with consecutively numbered, sealed opaque randomisation envelopes containing the assigned treatments: the two gestational strata will be differentiated using different colours. The envelope will be opened after written consent has been obtained and the infant has become eligible for the trial, and the assigned treatment will be immediately applied to the infant.

The randomisation procedure is as follows:

- a) Ensure that one machine of each type (FP/Dolphin) is available for use within 10 minutes;
- b) Confirm that the infant meets ALL inclusion criteria;
- c) Confirm that infant does NOT meet ANY exclusion criterion; and
- d) Confirm that informed consent has been received.

If all of the steps are confirmed, the infant's gestational group is identified, to determine the correct stratum, and the next randomisation envelope for that infant will be opened.

4.3. ***Blinding***

Blinding of intervention is not possible, as the machines are visibly different. Some blinding of outcomes assessment will be performed – see item 4.5 Measurement of Outcomes.

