Duration of CPAP (hours), for those not failing CPAP treatment, is the only continuous secondary outcome this is expected to be non-normally distributed and will therefore be assessed using Wilcoxon's rank sum test, with stratum-specific contributions aggregated using Elteren's extension to the Wilcoxon test.^[31]

The remaining secondary outcomes are dichotomous and will be tabulated and compared using stratum-specific relative risks (RRs); the homogeneity of stratum-specific RRs will be assessed using Cochran's Q and the I^2 tests^[32].

Software: All analysis will be conducted in SAS/STAT® 9.4, except for the calculation of stratum-specific and pooled relative risks, which will be performed in RevMan 5.3.^[33]

6. **Clinical protocol:**

6.1. **Interventions**

This study compares routine CPAP care on existing machines with CPAP care on a new machine that uses a re-usable humidifier and tube set.

Routine CPAP care will be on a Fisher & Paykel [FP] CPAP machine which includes separate oxygen and medical air intakes, a FP blender, and a disposable FP humidification chamber and tube set including a heater wire (Fisher & Paykel Healthcare Ltd, Auckland, New Zealand; hereafter referred to as FP CPAP). The new machine (hereafter referred to as the 'Dolphin CPAP') includes an oxygen intake, an on-board air compressor, built in Massimo pulse oximeter (not used in this study – see para 4.5 above), and an autoclavable humidifier and tube set.

6.2. **Treatment protocol features that are common to both arms**

The following systems will be common to both groups regardless of treatment allocation:

- Baby interface: An identical FP infant interface will be used for both groups of babies; this may require the creation of a special adaptor to permit use of the FP interface with the Dolphin CPAP tube set if the FP interfaces for non-FP connectors is not identical to the FP interface for FP tube sets;
- Pulse oximetry: The FP CPAP does not include built-in pulse oximetry, while the Dolphin CPAP does. To ensure consistency in measurement of pulse oximetry, Ramaiah Medical College will use a single pulse oximeter (built into the Mindray MEC 3000), for monitoring SpO₂ on all infants regardless of the treatment allocation. This ensures that any measurement error in SpO₂ will be non-differential.

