As an exploratory study, with a small planned sample size determined by time available for recruitment rather than a definitive assessment of a pre-determined clinically significant difference in endpoints, it was decided that no adjustments would be made for multiple comparisons of secondary endpoints, many of which were sentinel events. Rather any statistically significant results would be assessed within the context of the primary endpoint result, and with full acknowledgement of the risks of multiple comparisons.

ENDS

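### SAP para 10b names no effect estimate or confidence limit for any dichotomous outcome, so zero events or a non-significant test in 51 infants leaves the size of a possible harm unstated

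*SAP*

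**What the plan says.** Protocol section 1 (Aim & Hypothesis) includes monitoring of side effects and adverse events in what the comparison of machines is meant to do. Protocol 3.3 says "Selected complications of treatment will be evaluated as sentinel outcomes". Protocol 5.2 plans that the dichotomous secondary outcomes be "tabulated and compared using stratum-specific relative risks (RRs"), with Cochran's Q and I² for homogeneity. Its software paragraph adds pooled relative risks, calculated in RevMan.

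SAP para 9 repeats the planned analysis. Para 10b, listed among the revisions to it, then gives three routes:

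- Dichotomous outcomes in general: Cochran-Mantel-Haenszel test, with the Breslow-Day test for homogeneity.
- No events in one stratum (CPAP failure, serious adverse event, intubation and ventilation, death): Fisher's exact test on the full data.
- "Where there were no events in either stratum": "no statistical test was performed". This covers septal damage, damage to the nares, pneumothorax, IVH/ICH/PVL, sustained FiO₂ of 60% or more, and oxygen dependence at 36 weeks in the younger stratum.

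Para 10b mentions no relative risk, risk difference or confidence interval. On sample size, SAP para 2a states "The achieved sample size was n=51" and discusses what could be detected for the primary outcome only. Para 11 opens "As an exploratory study, with a small planned sample size determined by time available for recruitment" and goes on to say how statistically significant secondary results will be read.

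**The concern.** The protocol planned an estimate of effect. The revision names tests, and no estimate is put in place of the relative risks. At this sample size a test says little about harm: an excess has to be very large before it reaches significance, and an outcome without events cannot be tested at all. What can still be learned is an upper bound on the risk in each arm and an interval for the difference, and para 10b specifies neither.

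At stake is the comparative safety statement for a new device. If the report gives only counts and p-values, the reader cannot see which rates of nasal injury, air leak or brain haemorrhage remain compatible with the data. The SAP gives guidance on reading significant secondary results but none on reading null or empty ones.

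**Working it through.** **Inputs**
- Total randomised: 51 (SAP para 2a). The split by arm is not stated. Protocol 4.2 says "Block randomisation with variable block sizes will be used within each of two gestational age strata", with block sizes 4, 6 or 8, so 25 and 26 is a reasonable assumption. Arms of 22 to 28 are shown as a range.
- Events: none in either stratum for the six outcomes (SAP para 10b), hence none in either arm.
- Confidence level: not given in the documents. Two-sided 95% is assumed, with one-sided 95% alongside.

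**1. The plan's own figure.** The documents give no figure for what zero events can exclude. The only sizing is for a continuous outcome in Protocol 5.1: n per arm = 2(1.96 + 0.84)²/0.63² = 39.6, rounded up to 40, with power 80.4%. This reproduces, but it says nothing about complications.

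**2. Exact (Clopper-Pearson) upper limit for 0/n.** Two-sided 95%: U = 1 − 0.025^(1/n). For n = 25, U = 1 − 0.8628 = 13.7%.

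| Infants in arm | Two-sided 95% | One-sided 95% |
|---|---|---|
| 22 | 15.4% | 12.7% |
| 25 | 13.7% | 11.3% |
| 26 | 13.2% | 10.9% |
| 28 | 12.3% | 10.1% |
| 40 (as planned) | 8.8% | 7.2% |

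**3. Risk difference, zero against zero.** Newcombe's interval uses the Wilson upper limit z²/(n + z²), with z² = 3.8415. For n = 25 this is 3.8415/28.8415 = 13.3%, and for n = 26 it is 3.8415/29.8415 = 12.9%. The 95% interval is therefore about −12.9 to +13.3 percentage points.

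**4. Where these limits are too low.** Oxygen dependence at 36 weeks applies only to infants born at 28 to 33 completed weeks. The number per arm is not given. If it were 10, 15 or 20, the two-sided limit would be 30.8%, 21.8% or 16.8%. Protocol 6.2 leaves the need for pneumothorax screening and cranial ultrasound to be determined under the clinical protocol, so fewer than 25 per arm may have been examined. The FiO₂ outcome is defined by holding SpO₂ at 90-95%. SAP para 2b reports that range in 54 of 224 readings (24.1%), so its zero may not be a fully ascertained zero.

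**5. What a test can show at this size.** With 25 and 26 infants and no events in one arm, Fisher's exact test gives p = 0.051 for 4 of 25 against 0 of 26, and p = 0.023 for 5 of 25 against 0 of 26. For 5 of 26 against 0 of 25 it gives p = 0.051. Five or six events against none are needed for significance, a rate of about 20% or more.

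**6. An outcome with events.** SAP para 6 reports three Dolphin failures and one Fisher-Paykel failure within 72 hours, log-rank p = 0.30. As a crude illustration, ignoring stratum and the two infants discharged early:
- Dolphin 25, Fisher-Paykel 26: relative risk (3/25)/(1/26) = 3.1. SE of the log = √(1/3 − 1/25 + 1 − 1/26) = 1.12, giving a Wald 95% interval of 0.35 to 28. Risk difference 8.2 points, Newcombe interval −8.8 to +26.4.
- Dolphin 26, Fisher-Paykel 25: relative risk 2.9 (0.32 to 26). Risk difference 7.5 points (−9.7 to +25.3).

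These figures do not show harm. They show that p = 0.30 is compatible with a large excess in either direction, and more so with the new machine.

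**The case against.** The case on the other side has several sound parts.

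- **No test is not no analysis.** A reader might infer that the six outcomes are left unanalysed. The SAP says only that no test was done. Para 9 carries over the commitment to tabulate and para 10b does not withdraw it. With no events in either arm a relative risk cannot be estimated and a test has nothing to work on, so leaving it out is right. This stands; the gap is the missing interval.
- **Silence is not a prohibition.** Para 10b does not say that relative risks will be dropped, and the protocol's sentence on pooled relative risks is not listed as revised. This stands in part. The tests appear as revisions to the relative-risk plan, and nothing commits the report to an estimate.
- **Nobody claims safety.** A reader might infer that the trial will present zero events as proof of safety. No text says so. Protocol 4.6 expects too few adverse events to analyse usefully, and SAP para 11 calls the study exploratory. The misreading is a risk only. Still, those statements do not say how an empty or non-significant safety result should be read.
- **More than p-values is available.** Failures are given by arm with a Kaplan-Meier curve, and Annex B records severity, outcome and relatedness of each adverse event. This stands, but none of it bounds a risk.
- **A single 14% does not fit all six outcomes.** This also stands. The figure depends on the assumed split and on every infant having been assessed.
- **Only reporting is affected.** The SAP was updated on 31 August 2019, after the trial ended in July 2018, and these are secondary outcomes. That limits the weight of the point but does not remove it.

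**Conclusion.** The point holds as a gap in what is reported. For outcomes assessed in all infants, and with arms of 25 and 26, zero events leaves a risk of up to about 13-14% in either arm compatible with the data (exact two-sided 95%), and a difference of about 13 points either way. Arms of 22 to 28 move the upper limit only between 15.4% and 12.3%. The limit is higher for oxygen dependence at 36 weeks and for any outcome assessed in only some infants. For the three against one early failures, the interval for the difference runs from roughly −9 or −10 to +25 or +26 points.

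This rests on an assumed arm split, a conventional 95% level, and complete ascertainment of the zeros. It does not support a claim that the new machine is harmful, that the SAP discards the safety data, or that testing zero events was wrongly omitted. It is a cheap improvement to the reporting of secondary outcomes and does not touch the primary analysis.

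**What to change.** Amend SAP para 10b as follows.

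1. For the six outcomes without events, report events over infants assessed in each arm, with exact (Clopper-Pearson) 95% limits and a Newcombe 95% interval for the risk difference. Use the number actually assessed as denominator, and the younger stratum only for oxygen dependence at 36 weeks.
2. For outcomes with events, restore the planned relative risk (or give a risk difference) with a 95% interval beside the p-value, stratified by gestational group where that can be estimated.
3. State that zero events, or a non-significant test, does not establish equal safety.
4. Note beside the sustained FiO₂ outcome that its definition depends on an SpO₂ target met in 24.1% of readings.

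The cost is a paragraph of SAP wording and a few table columns, with no new data. The downside is a less favourable safety statement.
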